6.4 Data monitoring and safety board (DMSB)

The trial is supervised by an independent Data Monitoring and Safety Board (DMSB). The tasks of the DMSB in the CeTeG trial are the following:

- The DMSB will review all serious adverse events (SAE) of all patients so far recruited to the trial every half a year.
- In case of more than 1 patient with toxic death per 20 patients recruited, all safety information is provided to the DMSB independently of the 6 months turn for SAE reviewing.
- The coordinating PI (LKP) can ask the DMSB at any time to review any data from the trial and to decide whether to proceed with the trial without changes, to modify the trial or to stop the trial entirely. It may be for example necessary to modify the trial if during the ongoing trial the results of another randomized trial define a new standard of primary GBM therapy which will have impact on the standard arm of the ongoing trial. The data provided to the DMSB for review may include so far unmonitored data. In case a decision has to be made regarding the stopping or continuation of the trial, an extra monitoring visit has to monitor the data relevant for this decision.
- All amendments for the trial protocol are provided to the DMSB.
- The DMSB is free to suggest any modifications regarding the trial (e.g. stopping of the trial, modifications of the protocol). The DMSB will convene by telephone conference every 6 months to discuss whether any action has to be taken. The last DMSB telephone conference on the 6 months schedule will be held about 1 year after the inclusion of the last patient, i.e. 4 months after the end of any trial-associated chemotherapy.

Set up, members and tasks of the DSMB are outlined in detail in the DMSB manual.

7. ADVERSE EVENT REPORTING

The definitions and reporting requirements of ICH Guideline for Clinical Safety Data, Management, Definitions and Standards for Expedited Reporting, Topic E2 will be adhered to. This is briefly described below.

7.1 Definitions

7.1.1 Adverse event definitions and classifications

Adverse Events

An adverse event is any untoward medical occurrence in a patient or clinical investigation subject administered a pharmaceutical product and which does not necessarily have to have a causal relationship with this treatment. An adverse event includes any unfavorable and unintended sign including an abnormal finding, symptom, or disease temporally associated with the study treatment as well as any occurrence that is new in onset or aggravated in severity or frequency from the baseline condition, or abnormal results of diagnostic procedures including laboratory test abnormalities whether or not related to the product.

The clinical manifestation of any failure of expected pharmacological action is not recorded as an adverse event. If, however, the event fulfils any of the criteria for a “serious” adverse event, it must be recorded and reported as such. Investigators should also report signs and symptoms when ever present that are associated with the progressive disease.

The ZKS Cologne as the institution responsible for data management collects all adverse events data and is responsible for SAE handling, documentation and reporting to the authorities.

Serious adverse event

A serious adverse event is any untoward medical occurrence with the study treatment at any dose that meets any of the following conditions:

- results in death excluding death due to progression of disease unless related to study treatment. Exception: if the investigator deems the tumor progression to be related to the use of the study drug.

- is life-threatening at the time of the event i.e. immediate risk of dying
- requires inpatient hospitalization or prolongation of existing hospitalization
- results in persistent or significant disability or incapacity
- results in congenital anomaly or birth defect
- is considered significant and serious by the investigator for any other reason

Medical and scientific judgment should be exercised in deciding whether expedited reporting is appropriate in other situations; for example, important medical events may not be immediately life-threatening or result in death or hospitalization but may jeopardize the patient or may require intervention to prevent one of the outcomes listed in the definition above. Any adverse event is considered a serious adverse event if it is associated with clinical signs or symptoms judged by the investigator to have a significant clinical impact.

Life-threatening:

The term “life-threatening” in the definition of “serious” refers to an adverse event in which the patient was at risk of death at the time of the event. It does not refer to an adverse event which hypothetically might have caused death if it were more severe.

Hospitalization:

Any adverse event leading to hospitalization or prolongation of hospitalization will be considered as serious, UNLESS at least one of the following exceptions is met:

- The admission results in a hospital stay of less than 12 hours.

OR

- The admission is pre-planned (i.e., elective or scheduled surgery arranged prior to the start of the study).

OR

- The admission is not associated with an adverse event (e.g., social hospitalization for purposes of respite care).

It should be noted that invasive treatment during any hospitalization may fulfill the criteria of 'medically important' and as such may be reportable as a serious adverse event dependant on clinical judgement. In addition where local regulatory authorities specifically require a more stringent definition, the local regulation takes precedent.

Disability:

Means a substantial disruption of a person's ability to conduct normal life functions.

Unexpected adverse event

An unexpected adverse event, the nature or severity of which is not consistent with the applicable product information (e.g., Investigator's Brochure for an unapproved investigational product or the package insert/summary of product characteristics for an approved product). Also, reports which add significant information on specificity or severity of a known, already documented adverse event constitute unexpected adverse events. For example, an event more specific or more severe than described in the Investigator's Brochure would be considered "unexpected".

Association with the use of the drug

An adverse event is considered associated with the use of the drug if the attribution is possible, probable or very likely by the definitions listed in Section 13.1.2.

Suspected unexpected serious adverse reaction (SUSAR)

The suspicious case of an unexpected serious adverse reaction is defined as Suspected Unexpected Serious Adverse Reaction (SUSAR) as EU-Directive 2001/20/EC. They require very rapid notification of the Competent Authorities. If the SUSAR is fatal or life-threatening the Ethics Committee and Regulatory Agency will be notified (e.g. by telephone, facsimile transmission, or in writing) as soon as possible but no later than 7 calendar days after first knowledge by the sponsor that a case qualifies, followed by as complete a report as possible within 8 additional calendar days. This report will include an assessment of the importance and implication of the findings.

All other suspected unexpected serious ADRs, which are not fatal or life-threatening, must be reported as soon as possible but no later than 15 calendar days after first knowledge by the sponsor that the case meets the minimum criteria for expedited reporting.

The initial reports submitted will contain at least: randomization number, a suspect medicinal product, an identifiable reporting source, description of SAE, and for which there is a reasonable suspected causal relationship, the sponsor's unique case identifier and the study protocol or EudraCT number. Follow-up information will be actively sought and submitted as it becomes available.

7.1.2 Documentation and assessment of adverse events

Adverse events contain as defined all diseases, clinical signs or symptoms, which appear after randomization of patients.

The **type** is determined as followed:

- continuous
- intermittent

The **maximum intensity** is defined as

- mild
- moderate
- severe

The **relationship to the trial medication** has to be described as

- certain
- probable
- possible
- unlikely

The **outcome is described** as follows:

- recovered
- improved
- unchanged
- worsened
- death
- unknown

7.2 Procedures

7.2.1 All adverse events

All adverse events that occur between the first study-related procedure and 30 days following the last study-related procedure (excluding follow-up) and medical conditions prevalent prior to the first study-related procedure will be recorded. All adverse events

must be followed to satisfactory resolution or stabilization of the events. Any adverse event meeting the definition of SAE must be reported using the SAE form.

All adverse events, regardless of seriousness, severity, or presumed relationship to study therapy, must be recorded using medical terminology in the source document and the CRF. Whenever possible, diagnoses should be given when signs and symptoms are due to a common etiology e.g., cough, runny nose, sneezing, sore throat, and head congestion should be reported as “upper respiratory infection”. Investigators must record in the CRF their opinion concerning the relationship of the adverse event to study therapy. All measures required for adverse event management must be recorded in the source document and reported according to sponsor instructions.

The coordinating principal investigator as the designee of the sponsor assumes responsibility for appropriate reporting of adverse events to the regulatory authorities and to the appropriate IEC/IRB. This includes the second assessment concerning seriousness, relatedness and expectedness regarding SAEs. Additionally the sponsor is responsible for the continuous evaluation of the risk/benefit ratio of the trial. Changes in the risk/benefit ratio have to be reported to the regulatory authorities and to the appropriate IEC/IRB within in 15 days of awareness.

Patients (or their designee, if appropriate) must be provided with a “study card” indicating the name of the investigational product, the study number, the investigator’s name and a 24-hour emergency contact number.

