Adverse events in man mainly affect the hematopoietic system with thrombocytopenia, leucocytopenia and anaemia. Myelosuppression occurs delayed, mainly after 4-6 weeks and can be cumulative. Further, medication with CCNU might lead to nausea and vomiting, more rarely to diarrhea. Occasionally, moderate hepatic dysfunction has been observed. In rare cases, pulmonary fibrosis, alopecia, stomatitis and minor neurological dysfunctions, e.g. apathia, ataxia and desorientation. In a few cases, irreversible damage of the optic nerve has been described in the combination with radiotherapy. CCNU can have carcinogenic, mutagenic and teratogenic effects.

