Before start of chemotherapy (concomitant TMZ or first cycle CCNU/TMZ: blood analysis obtained in Baseline can be used if not longer than 5 days old)

 - Assessment of survival
 - vital signs,
 - physical and neurological examination,
 - concomitant medication,
 - Karnofsky PS,
 - complete blood count and CRP,
 - serum chemistry and urine analysis,
 - coagulation,
 - CTCAE evaluation

Throughout all treatment courses of TMZ and CCNU/TMZ starting with radiotherapy a differential blood count has to be determined weekly by the general practitioner of each patient. The results have to be faxed within 24 hours to the treating center for review. In case pathological laboratory values are regarded by the local investigator to have medical consequences (e.g. grade 4 neutropenia requiring prophylactic antibiotic treatment) the differential blood count has to be repeated at the study center.

- **MRI/ progression assessment visits every 12 weeks (+/- 5 days) after randomization during study treatment and follow up until end of study**
- (Follow-up of all patients ends 36 months after the inclusion of the last patient. All patients in the trial are followed until this time point.)
 - vital signs
 - physical and neurological examination

- concomitant medication (all medication during the treatment phase, during follow-up this includes only the tumor-related medication)
- further tumor-directed therapy (surgery, radiotherapy, chemotherapy): day of start of further therapy, day of progression for each therapy
- Karnofsky PS
- Mini-Mental-Status evaluation
- quality of life questionnaire
- contrast-enhanced MRI scan
- NOA-07 test battery (only every 24 weeks)
- complete blood count and CRP
- Blood sampling for translational studies
- serum chemistry and urine analysis
- coagulation
- CTCAE evaluation
- Assessment of progression/survival

Table 2: Schedule of Study procedures

	Screening visit Week 1-3	Baseline visit Week 3-5 ⁽²⁾	Treatment phase		After 6 courses of CCNU/TMZ or TMZ
			At the beginning of each course of CCNU/TMZ or TMZ	MRI/progression assessment visit every 12 weeks ⁽¹⁾	MRI/progression assessment visit every 12 weeks ⁽¹⁾
Clinical examination					
Informed consent for MGMT and reference neuropathology ⁽³⁾⁽³⁾	x				
Informed Consent for trial participation		x			
Results of MGMT testing and ref. neuropathology		x			
I / E criteria, demographics and medical history		x			
Evaluation of preexisting conditions in analogy to CTCAE		x			

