6.3 Safety Evaluations

Safety is monitored continuously throughout the trial as detailed in Table 2 “Time and Schedule of Events”. The study will include the following evaluations of safety and tolerability:

Adverse Events: Adverse events will be reported throughout the study at each visit. Adverse events will be followed by the investigator.

Clinical Laboratory Tests: Laboratory tests at each visit will be performed at the Laboratory of the treating University Medical Center. Between visits, weekly laboratory testings are performed by the general practitioner or oncologist of the patients and results are to be faxed within 24 hours to the local investigator. All laboratory reports will be reviewed by the investigator. This review must be documented, and any clinically relevant changes occurring during the study must be recorded in the adverse event section of the CRF.

Vital Signs

Physical and neurologic examination: Any clinically significant abnormalities persisting at the end of the study will be followed by the investigator until resolution or until reaching a clinically stable endpoint.

Karnofsky performance score: Karnofsky performance score is outlined in appendix 1

NOA-07 test battery: the NOA_07 test battery is outlined in section 9.2.7.

MMST: The MMST is outlined in appendix 2

General safety monitoring: The management of SAE within the study group will be according to ICH GCP, i.e. depending on the criteria expected/unexpected, suspected/

not suspected, dead/alive SAEs have to be announced to the sponsor within the legal time frame. Similarly, the sponsor will announce SAEs to the authorities within the legal time frame. For details see chapter 7 (adverse event reporting). Safety is independently monitored by the Data monitoring and safety board as detailed below.

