7.2.2 Serious Adverse Events

Reporting of Serious Adverse Events

All serious adverse events occurring during clinical studies and within 30 days following the last study-related procedure must be reported by the investigator **within 24 hours** of their knowledge of the event by fax to the following address:

ZKS Cologne
[name]
Telefon: [name]
[contact]

The ZKS Cologne is responsible for SAE handling and documentation, SAE quality assurance, SAE- reporting to BfArM / CA / investigators and development of SAE database.

A serious adverse event form must also be completed within 24 hours of the awareness and forwarded to the above mentioned address. Each serious adverse event must be followed up until resolution or stabilization, by submission of updated reports. All serious adverse events that have not resolved by the end of the study, or that have not resolved upon discontinuation of the patient's participation in the study, must be followed until any of the following occurs:

- the event resolves
- the event stabilizes
- the event returns to baseline, if a baseline value is available
- the event can be attributed to agents other than the study drug or to factors unrelated to study conduct, or
- when it becomes unlikely that any additional information can be obtained (patient or health care practitioner refusal to provide additional information, lost to follow up after demonstration of due diligence with follow-up efforts)

Reporting of pregnancy

In the event of a pregnancy occurring in a patient or in a partner of a male patient after the first dose of the trial medication was applied has to be recorded on a pregnancy

form. This form must be reported by the investigator **within 24 hours** of their knowledge of the event by fax to the following address:

ZKS Cologne
[name]
Telefon: [name]
[contact] [name]

Monitoring of the patient will be continued until the conclusion of the pregnancy.

Development Safety Update Report – DSUR (former Annual Safety Report)

Once per year, the sponsor or PCI will supply a report on the safety of trial subjects with all available relevant information concerning patient safety during the reference period to the competent supreme federal authority and the competent authorities of all other member states of the EU or EEA where the trial is being conducted. This report will also be supplied to the responsible ethics committee.

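### The adverse event recording window is contradictory: 7.2.1 closes it 30 days after an undefined last procedure and excludes follow-up, while 6.3 and Table 2 run to study end

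*Protocol*

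**What the plan says.** Five places in the protocol bear on when adverse events (AEs) are recorded.

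- Section 7.2.1 gives the period as "All adverse events that occur between the first study-related procedure and 30 days following the last study-related procedure (excluding follow-up".
- Section 7.1.2 starts later: "Adverse events contain as defined all diseases, clinical signs or symptoms, which appear after randomization of patients".
- Section 6.3 has no end before study end: "Adverse events will be reported throughout the study at each visit". For laboratory findings it adds that "any clinically relevant changes occurring during the study must be recorded in the adverse event section of the CRF".
- Section 6.1 plans "MRI/ progression assessment visits every 12 weeks (+/- 5 days) after randomization during study treatment and follow up until end of study". The list for these visits, and Table 2, include a blood count and a CTCAE evaluation.
- Section 7.2.2 covers serious events: "All serious adverse events occurring during clinical studies and within 30 days following the last study-related procedure must be reported". It does not exclude follow-up.

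On timing of toxicity, Section 1.4.2 says of CCNU: "Myelosuppression occurs delayed, mainly after 4-6 weeks and can be cumulative". A CCNU/TMZ course lasts 42 days with the last dose on day 6. An adjuvant TMZ course lasts 28 days with the last dose on day 5.

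**The concern.** The protocol does not say which procedure is the last study-related one, and its sections disagree on whether recording continues in follow-up. This is more than a detail for the analysis plan, because it decides which events reach the database at all.

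Two things are at stake. First, Section 2.2 names late as well as acute toxicity as an objective. A site that stops as 7.2.1 allows need not record non-serious late events. Section 1.4.2 lists pulmonary fibrosis and optic nerve damage among the effects of CCNU, and the phase II trial described in Section 1.1 saw a grade 2 lung fibrosis. Second, acute toxicity is a secondary endpoint compared between arms whose courses differ in length and whose nadirs differ in timing. A 30-day tail hung on an unstated anchor may cover the last course fully in one arm and not in the other.

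**Working it through.** **1. The rules side by side**

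| Section | Start | End |
|---|---|---|
| 7.1.2 | randomization | not stated |
| 7.2.1 | first study-related procedure | 30 days after the last one, follow-up excluded |
| 6.3 | not stated | throughout the study, each visit |
| 6.1, Table 2 (CTCAE) | baseline | every 12 weeks to study end |
| 7.2.2 (serious events) | during the study | 30 days after the last procedure, follow-up not excluded |

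Both ends differ. Section 3.5 calls the 12-weekly visits after completion or withdrawal follow-up, so under 7.2.1 they cannot serve as the last procedure.

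**2. Treatment duration, as a check on the inputs**

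Experimental arm: 6 x 42 / 7 = 36 weeks. Standard arm: 6 + 4 + 6 x 28 / 7 = 34 weeks. Both agree with the synopsis.

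**3. How far the readings differ in follow-up**

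Minimum follow-up is 36 months from randomization: 36 x 52 / 12 = 156 weeks. Radiotherapy starts at most 2 weeks after randomization. Even if the last procedure is put at the end of the last course, 7.2.1 closes 30 / 7 = 4.3 weeks later. For a patient who survives, with no delays, the time left is

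- experimental arm: 156 - 2 - 36 - 4.3 = 113.7 weeks;
- standard arm: 156 - 2 - 34 - 4.3 = 115.7 weeks.

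That is more than two years (104 weeks) in either arm.

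**4. Where the window closes in the last course**

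Closing day = course day of the last procedure + 30. With CCNU on day 1, 4-6 weeks later is day 1 + 28 = 29 to day 1 + 42 = 43. Weekly counts are assumed on days 1, 8, 15 and so on.

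| Last procedure taken as | CCNU/TMZ (42 days) | Adjuvant TMZ (28 days) |
|---|---|---|
| Course visit, 5 days before start | not allowed | -4 + 30 = day 26 |
| Course visit, day 1 | 1 + 30 = day 31 | 1 + 30 = day 31 |
| Last dose | 6 + 30 = day 36 | 5 + 30 = day 35 |
| Last weekly count | 36 + 30 = day 66 | 22 + 30 = day 52 |
| Last day of course | 42 + 30 = day 72 | 28 + 30 = day 58 |

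In the experimental arm the first two available anchors (days 31 and 36) close inside the day 29-43 span, and the last two cover it. In the standard arm every anchor covers the course except the visit held 5 days early, which Section 6.1 permits and which closes 2 days short.

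**5. The nearest scheduled evaluation**

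The week-36 visit is 252 days after randomization. If radiotherapy starts r days after randomization, course 6 starts on day r + 5 x 42 = r + 210, so the visit falls on course-6 day 252 - (r + 210) + 1 = 43 - r. For r from 0 to 14 this is day 43 down to day 29, or day 24 to 48 with the 5-day tolerance. Without delays, a blood count and CTCAE evaluation therefore fall in or near the nadir span of course 6.

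**The case against.** A reader might infer that the 30-day limit undercounts toxicity in the experimental arm only and makes CCNU/TMZ look safer than it is. The documents do not support that.

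- Weekly counts are required throughout every course, and Section 11.7 groups weekly laboratory tests with trial procedures. On that reading the window reaches about day 66-72 and covers the nadir.
- Section 6.3 enters clinically relevant laboratory changes as AEs without a 30-day limit, and the synopsis has an AE questionnaire for each course, with no exception for the last.
- The standard arm can also close short (day 26 of 28).
- Section 1.4.2 says only that myelosuppression may be cumulative. It does not say that the last course is the worst, and Section 5.1.3.1 lowers the CCNU dose after late nadirs.
- Uncovered calendar days are not missed events. Neither they nor the phase II myelotoxicity rate, which is per patient over a whole trial, gives the size of an undercount.

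It can also be said that a site recording AEs at every visit to study end satisfies all the sections, and that late neurotoxicity has its own tests.

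All of this stands against the stronger claim. It does not remove the contradiction. A site that stops as 7.2.1 allows also has the text on its side, and the other capture routes are largely the passages that 7.2.1 contradicts. Nor is the week-36 visit a dependable backstop: it fits only without course delays, and for a patient who stops early the later 12-weekly visits are follow-up.

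**Conclusion.** The point holds as a contradiction in the AE window at both ends, with an undefined anchor. Its firm consequence is that 7.2.1, taken literally, leaves non-serious late toxicity unrecorded for more than two years in a surviving patient, against the objective in Section 2.2. The consequence for acute toxicity is conditional. If a site anchors on the last course visit or last dose, recording closes on day 31 or 36 of the last 42-day CCNU/TMZ course, inside the nadir span, whereas from the last dose the 28-day TMZ course is fully covered (day 35). If the weekly counts are the anchor, there is no gap. Any gap affects only the last course and mainly, not solely, the experimental arm. The documents give no figure for its size.

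The day counts assume dosing from day 1, no course delays and weekly counts from day 1. That Section 9.4 names no analysis window is not a criticism, since the statistical analysis plan may do so; but it cannot recover events that were never collected.

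**What to change.** State one window, in the same words, in Sections 6.3, 7.1.2, 7.2.1 and 7.2.2.

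- **Start:** one start for both arms, with randomization as the start for the arm comparison. If events between the first study-related procedure and randomization are still to be recorded, say so and keep them out of the comparison.
- **End, all AEs:** a fixed number of days after the last dose of study chemotherapy, equal in both arms and long enough for a 42-day course plus 30 days. For example, 66 days gives day 6 + 66 = day 72 of a CCNU/TMZ course and day 5 + 66 = day 71 counted from the start of a TMZ course. Where CCNU on day 1 was the last dose, it gives day 67, still past day 43. An anchor on the last dose also covers patients who stop during concomitant TMZ.
- **After that:** serious and treatment-related AEs at the 12-weekly CTCAE evaluations already in Table 2, to study end.
- **Analysis:** use the common window for the toxicity comparison in Section 9.4.

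The cost is protocol wording, a CRF instruction and a few more weeks of AE entry per patient; no new assessment is needed. Section 9.1 shows that the current text postdates the last inclusion by at least 14 months, so for most patients the last-course part would be completed from the weekly counts already faxed to the centers, while the follow-up part can still be applied prospectively.
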